2. 57 Gy at 1.8 Gy per fraction (IMRT) with optional nested GTV dose to total not to exceed 72 Gy at 2.2 Gy per fraction (Example Figure 1), or
3. 51 Gy at 1.5 Gy per fraction twice daily (bid) to the CTV followed by optional GTV boost at 1.5 Gy bid to total dose.

Dose escalation  $\geq 60$  Gy to achieve local control of gross disease that will not be resected (patient remains inoperable in surgical consultation prior to completing radiation treatment. patient has gross disease in sites not resected in standard surgery such as IMC nodes and supraclavicular nodes) will be at the discretion of the treating physician (See example, Figure 1)

*Guidelines for GTV dose escalation:*

- 60-66Gy to gross disease  $<1$  cm, up to 72 Gy to gross disease  $\geq 1$  cm when standard normal tissue constraints can be met) can be delivered to regional lymph nodes that will not be resected at the time of surgery.
- Based on the data by Huang et al 3, dose to potentially resectable disease (that routinely removed in a modified radical mastectomy: breast and level I/II lymph nodes) will be limited to 54 Gy at 2 Gy/fraction or 57 Gy at 1.8/fraction to limit surgical complications in operable patients.

Dose regimen (of the three listed options above) will be at the discretion of the treating oncologist. Nearing the conclusion of 50-54/57/51 Gy patients will be reassessed for operability by the attending physicians and/or the surgeon.

Protocol based radiation dose to the CTV incorporates regimens in current practice. While an argument for a palliative dose strategy such as 30 Gy in 10 fractions of 3 Gy per fraction could be made for this population, there is little to no data using Capecitabine with fraction sizes larger than 2.0 Gy per fraction, and it has been suggested by the gastro-intestinal radiation service at MDACC 13 that higher dose is needed to effectively test a radiosensitizer. .

Treatment will be continued on the basis of tumor reassessment and/ or disease status

performed at 1 week intervals. All radiation planning will be peer-reviewed in a weekly breast radiation planning QA conference. Radiation to a second site (metastatic disease excluding whole brain) during or overlapping with protocol specified therapy is permitted.

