## 6.0 Study Design

This is a single center, neoadjuvant phase II study (Schematic Appendix D). Eligible subjects must be women with a diagnosis of invasive breast cancer with primary or recurrent gross disease in the breast or chest wall or lymph nodes that is progressive, persistent, or minimally responsive to chemotherapy. Patients with oligometastatic disease (generally ≤ 3 distant sites, but at the discretion of the treating physician) who would benefit in terms of symptom palliation (pain, drainage, or emotional duress) are eligible. After the initial screening, patients who consent to translational studies will have the following samples stored or analyzed: serum (for CTCs, 1 tube – cell save; serum, 1 tube speckled top) and urine collection, and core needle biopsy (flow cytometry).

Size of tumor lesions in the breast and nodal basins will be documented based on initial clinical exam and imaging (planning CT) using recist criteria (Appendix F). All RECIST measurements will be made by a single physician, [name]. IBC status will be recorded. Palliative vs pre-operative intent (based both on extent of metastatic disease and primary disease) will be recorded by the treating physician (Initial Assessment Form Appendix G). Subsequently, eligible, consenting women will receive pre-operative radiation with concurrent capecitabine. Capecitabine is commercially available and the commercially available supply will be used. Neither the drug nor the radiation will be free. Patients receiving Herceptin (trastuzumab) are eligible for participation and may receive concurrent Herceptin plus radiation and Xeloda (capecitabine). Chemotherapy administered after protocol treatment (after the last dose of radiation and capecitabine) is acceptable. Surgical consultation or follow up will be requested to be scheduled after 45 Gy and before the final fraction of radiation for patients treated with pre-operative intent. The treating oncologist may change this status to palliative if the clinical course makes the surgical consult unnecessary/patient is clearly unresectable in the judgment of the treating oncologist.

After completion of 45 Gy and within 15 days of completing treatment the total protocol specified dose to the breast, in patients who consent to translational studies a second core needle biopsy (for banking and flow cytometry), serum (for CTCs, serum) and urine collection will be performed.

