Linear accelerator based CT imaging (CT on rails or cone beam CT) or re-CT-simulation will be performed after 45 Gy to assess for the need to re-plan secondary to response. Tumor size will be documented using recist criteria based on these images. Additional accelerator based CT imaging is acceptable as clinically indicated.

Definitive or palliative local therapy with surgery when indicated will be performed after completion of the combined regimens. If the patient is deemed operable the first follow-up visit will occur after surgery. If the patient is deemed inoperable the first follow-up visit will occur after concurrent Capecitabine and radiation therapy. Subjects will be followed every 3 months (+/- 1 month) post treatment times 1, then every 6 months (+/- 1 months) times 1, then every 12 months (+/- 2 month) times 2. PET/CT scan or ultrasound will be performed in conjunction with the first follow up visit. For patients treated to definitive dose for gross unresected disease (any treatment field receiving a total of > 60 Gy in the mosaic prescription), all sites receiving > 60 Gy will be scored as complete response, partial response, noresponse/progressive disease based on imaging and exam after this visit and when evaluable and all subsequent visits. Subsequent radiologic studies will be at the discretion of the treating oncologist as dictated by standard of care. Toxicity will be recorded at each visit using the RTOG criteria.

Capecitabine dose reduction criteria are as follows:

Capecitabine will be held for patients experiencing grade 3-4 Capecitabine related

toxicities until symptomatic improvement (Grade 1). Radiation therapy will not be held for Capecitabine related toxicities. Patients will then be restarted with reduced dose of Capecitabine (level-1). Level -1 (25% dose reduction) = 600 mg/m^2 BID. If patients develop additional grade 3-4 toxicity in spite of dose reduction, the chemotherapy will be permanently discontinued.

Correlation will be made between Change in CTC level and change in percent of CD44+CD24lo or ALDH1+ cells in the tumor biopsy. Change will be correlated with clinical and pathologic response (in patients who undergo surgery)

Approximately 60 subjects will be enrolled. Assuming an average accrual rate of 3-4 subjects per month, the duration of accrual will be approximately 20 to 26 months.

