##### **11.6.2 Secondary Analysis**

Patients who were deemed at time of enrolment to be inoperable or questionably inoperable (requiring flap closure with doubt regarding ability to obtain negative margins based on surgical oncology assessment) who have objective clinical response and receive mastectomy or are offered mastectomy but refuse will be considered having converted to operable. Patients who are resectable but considered inoperable based on advanced locoregional disease or M1 disease who have a mastectomy and no FDG-avid disease on PET at 3 month follow up will also be considered having converted to operable.

A secondary indicator of treatment efficacy is pCR. pCR is defined as the lack of any invasive disease in the breast and lymph nodes. A pathologist at the University of Texas M.D. Anderson Cancer Center will perform accurate sampling and review of all cases that have surgery. pCR will be assessed at the time of surgery following the completion of all protocol specified neoadjuvant chemotherapy, which will be approximately 26

weeks following the start of neoadjuvant chemotherapy. Subjects with unknown or missing response and those who do not convert to operable will be included in the primary efficacy analysis as non-responders.

A secondary analysis will calculate response rate based on subjects with evaluable tumor response only; i.e., the denominator will only include subjects with CR, PR, SD, or PD and will not include those with unknown or missing best response.

Exact 95% confidence limits for the clinical response rate will be calculated.

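### The second route to conversion in 11.6.2 requires no response, so it can credit the regimen with a conversion it did not produce; 6.0 also allows ultrasound where that route needs a PET

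*Combined protocol and SAP*

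**What the plan says.** Section 11.6.2 (Secondary Analysis) gives two routes to conversion.

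- **First route.** Patients judged inoperable or doubtfully operable at enrolment "who have objective clinical response and receive mastectomy or are offered mastectomy but refuse will be considered having converted to operable".
- **Second route.** "Patients who are resectable but considered inoperable based on advanced locoregional disease or M1 disease" and "who have a mastectomy and no FDG-avid disease on PET at 3 month follow up will also be considered having converted to operable".

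Three other provisions bear on the second route.

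- **Second-site radiation (4.1).** "Radiation to a second site (metastatic disease excluding whole brain) during or overlapping with protocol specified therapy is permitted".
- **Systemic therapy (6.0).** "Chemotherapy administered after protocol treatment (after the last dose of radiation and capecitabine) is acceptable". Concurrent trastuzumab is also allowed, and patients with oligometastatic disease may enrol.
- **Imaging (6.0).** "PET/CT scan or ultrasound will be performed in conjunction with the first follow up visit". For patients deemed operable, that visit comes after surgery. Later imaging is left to the treating oncologist.

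Conversion is the first item in the secondary efficacy objectives (1.0).

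**The concern.** The objective in 1.0 is conversion after the protocol regimen, so a reader will take the rate as something radiation plus capecitabine achieved. The first route supports that reading because it demands a response. The second does not: its two conditions are an operation and a scan that normally comes after the operation. A combined rate mixes conversions that document a response with conversions that need not.

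The imaging provision can act the other way. A second-route patient may have benefited fully and still fail the definition because ultrasound was used.

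The background figures that invite comparison lie close together. In 3.2, 84% (32 of 38) had a mastectomy after radiation; in 3.5, 82% and 91% became operable with capecitabine and radiation. A shift of several points from the definition alone could change how the trial's rate reads beside them.

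**Working it through.** The plan states no target, sample size or precision for conversion, so there is no figure to reproduce. The check is a comparison of the text, followed by illustrative arithmetic.

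**1. The two routes side by side (11.6.2)**

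| Criterion | First route | Second route |
|---|---|---|
| Starting status | Inoperable or doubtfully operable | Resectable, but held inoperable for locoregional extent or M1 disease |
| Objective clinical response | Required | Not mentioned |
| Mastectomy | Done, or offered and refused | Must be done |
| PET at 3 months | Not mentioned | No FDG-avid disease |

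The second route also asks for no comparison with a baseline PET.

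**2. Timing.** Section 6.0 places surgery after the combined regimen, the first follow-up of operable patients after surgery, and a follow-up at 3 months (plus or minus 1 month). The PET therefore normally follows the mastectomy. Avid disease in the breast has been removed by then, whatever the regimen did to it.

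**3. What else can clear the scan.** Second-site radiation, trastuzumab and later chemotherapy can each act on disease outside the breast before the PET. A resectable M1 patient whose breast tumour is stable, who has a mastectomy and whose only avid metastasis was irradiated as a second site meets the rule as written.

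**4. Possible over-count.** All three inputs are assumptions:

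- s = share of patients under the second route (0.1 to 0.5)
- p = conversion rate if response were required throughout (0.5 or 0.8)
- q = share of second-route patients without response who still have a mastectomy and a clean PET (0.25 to 0.75)

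Rate as written = (1 − s)p + s[p + (1 − p)q] = p + s(1 − p)q, so the excess is s(1 − p)q.

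| s | q | p | Excess (points) | Patients of 60 |
|---|---|---|---|---|
| 0.1 | 0.25 | 0.8 | 0.5 | 0.3 |
| 0.3 | 0.5 | 0.8 | 3.0 | 1.8 |
| 0.3 | 0.5 | 0.5 | 7.5 | 4.5 |
| 0.5 | 0.75 | 0.5 | 18.8 | about 11 |

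Section 10.0 words this endpoint among patients who go on to surgery, while 1.0 does not, so the denominator of 60 is itself an assumption.

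**5. Over-count and ultrasound together.** Assume 40 patients count for conversion and 10 are on the second route. Assume further that all 10 have a mastectomy and would have a clean PET, and that f = 2 to 4 of them had no response. Let u be the share imaged only by ultrasound, unrelated to response.

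- Counted: 10(1 − u). With response: 10 − f. Net error: 10(1 − u) − (10 − f) = f − 10u patients.
- u = 0: +2 to +4 patients, or 2/40 = 5 to 4/40 = 10 points too high.
- u = 0.5: 2 − 5 = −3 to 4 − 5 = −1 patients, or 7.5 to 2.5 points too low.
- The error is zero at u = f/10, that is 20% to 40% imaged by ultrasound only.

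The sign depends on u, which the documents do not give.

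**The case against.** The strongest defence is that the routes address different barriers. Second-route patients are kept from surgery by the extent of disease, not by a breast tumour that cannot be resected, and a PET without avid disease addresses extent directly. In two respects this route is the stricter one: the mastectomy must actually be done, and the scan must be entirely clear. A clean PET can also be the regimen's work. Section 4.1 provides for protocol radiation to internal mammary and supraclavicular nodes that standard surgery leaves in place, and capecitabine acts systemically. Requiring a response in this route could then exclude a patient whose breast tumour is stable but whose extent-limiting disease has cleared.

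Further, conversion is secondary, with no decision rule; the criteria for further study in 11.1 are response rate and toxicity. Neither the 82% nor the 91% in 3.5 is stated to require a response, so a stricter definition might compare less well with them. On imaging, 11.6.2 itself names PET and 6.0 permits it. The Time and Events Table (Appendix E) is not in the text available for this review and may settle the modality.

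Most of this stands. It shows that a clean PET does not imply absence of response, and that making response mandatory is a debatable trade-off. It does not show that the second route documents a response, and 11.6.2 does not ask for the tabulation that would separate the cases. Nor does it change the fact that 6.0, as worded, is satisfied by an ultrasound with which 11.6.2 can do nothing.

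**Conclusion.** The point holds in limited form. As written, the second route can count a conversion without a response to the regimen, and 6.0 can leave a second-route patient without the PET the definition needs. The size and net direction of the bias are unknown. The 0.5 to 18.8 points, and the swing between 10 points too high and 7.5 too low, rest entirely on assumed inputs and show only that the effect could be material.

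Four stronger readings are tempting and are not supported.

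- **That the conversion rate is inflated.** With ultrasound-only follow-up applied evenly, it can as easily be too low.
- **That the second route covers patients who were operable all along.** The text says resectable but considered inoperable, for stated reasons of disease extent.
- **That the second route measures only surgery and other treatment.** Protocol radiation to unresected nodes and the systemic effect of capecitabine can also produce a clean PET.
- **That the route inflates the primary response rate.** 11.6.1 defines that endpoint by RECIST, and a second-route conversion is not a RECIST response. 11.6.2 does count non-converters as non-responders in the primary analysis; that sentence sits badly with 11.6.1 and needs reconciling in its own right.

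**What to change.** **In 11.6.2:**

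- Report the conversion rate by route as well as combined.
- Cross-classify second-route conversions by the RECIST response already planned (after 45 Gy in 11.3, and 4 weeks after radiation in 11.6.1), stating which assessment preceded surgery. Cross-classify them also by any non-protocol therapy given before the PET: second-site radiation, trastuzumab or chemotherapy.
- Base statements about the regimen's effect on conversion on conversions with documented response, and show the current combined definition alongside.
- Add a sensitivity analysis in which second-route patients without a PET are not assessable, rather than not converted.

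**In 6.0:** reconcile the follow-up imaging with 11.6.2, so that second-route patients have at the 3-month visit the PET that the definition requires. Check Appendix E for consistency.

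**Cost.** The tabulations use RECIST assessments already planned, plus a record of non-protocol therapy before the PET; no patients are added. The rate attributed to the regimen will be somewhat lower than the combined rate, by an amount that cannot be predicted from the documents. The subgroups will be small and their estimates imprecise. Second-route patients lose the ultrasound alternative at that visit, with whatever burden the PET brings.

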## Protocol Body

### 1.0 Objectives

#### Primary

The primary objective of the study is to determine the rate of response by RECIST criteria (Appendix F) in all patients who receive treatment. This includes the following:

- Pre-operative or palliative concurrent radiation with capecitabine to the breast and at risk or involved regional lymph node basins

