## 8.0 Selection of Patients

### 1. 8.1 Inclusion Criteria

1. Histological confirmation of invasive breast cancer
2. No contraindications to receiving a course of radiation treatment (pregnancy, prior radiation to the volume with disease, or systemic disease in which radiation therapy is an absolute contraindication).
3. Patients who have chemo-refractory gross disease in the breast causing symptoms (pain, drainage, duress) OR

gross disease in the breast ( $\geq T3$ ) and/or lymph node(s) progressive, persistent, or minimally responsive to chemotherapy deemed inoperable or questionable inoperable  
OR

recurrent gross disease in a previously unirradiated breast or on the chest wall or in the regional lymphatics (core biopsy will not be offered to patients without gross disease in the breast).

4. Are able to swallow and retain oral medication (intact pill).
5. Age over 18.
6. Female gender

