# **11.0 Power Calculations and Statistical Analysis**

## **11.0 Power Calculations & Statistical Analysis**

### **11.1 Hypotheses**

The primary objective of this study is to determine response rate after completion of all protocol specified neoadjuvant chemotherapy+ concurrent radiation. The regimen will be considered of interest for further study if the response rate is at least 80% and the grade III toxicity excluding acute skin toxicity is <20%.

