### **11.3 Sample Size Considerations and Interim Analyses**

The primary objective of this study is to determine the efficacy of pre-operative radiation with concurrent capecitabine in patients who have experienced a minimal response or progression after standard neoadjuvant chemotherapy. Efficacy will be determined by tumour response (complete response + partial response) as measured by RECIST criteria. Tumour response will be assessed after 45 Gy. Those who do not finish will be considered non-responders. Toxicity will be assessed at the same time. Surgical complications will be assessed independently within 6 weeks of surgery. Only grade three toxicity will be considered in the stopping rules. This study will be monitored for both efficacy and safety. Safety will be determined by the rate of grade 3 or higher toxicities, excluding acute skin toxicity. This regimen will not be considered of interest for further study if there is a high probability that the response rate is less than 80% or the severe toxicity rate is greater than 20%. Priors regarding response are based on combined retrospective data from three studies of 135 total patients treated for gross disease in the breast at our institution and detailed in the background (sections 3.2 and 3.5). Local control (a surrogate for response) at 5-years in patients treated for gross IBC disease in the breast with radiation alone was 75% (N = 42, unpublished). In 38 similar patients with non-inflammatory breast cancer local control was 70% at 5 years. In an unpublished retrospective analysis of 55 patients treated with the regimen proposed herein, 5-year local control was 85% (Perkins, SABCS abstract, 2007). There are limited and poor data regarding radiation alone toxicity in this exact cohort. The priors for toxicity were based on aggressive xrt in post-mastectomy patients (N = 192). In these patients, we expect a 15% rate of Grade 3 toxicities in patients receiving 60Gy and a 29% rate of Grade 3 toxicities in patients receiving 66Gy, and unpublished data. Clinically we are currently limiting the use of the latter regimen based on the impression that this is unacceptably high toxicity, so we are targeting a Grade 3 toxicity rate of no more than 20%. All patients who receive any treatment will be included in the analyses of both efficacy and safety. Patients who are not evaluable for response will be considered non-responders. The final analysis will be an Intent to Treat analysis. A total of 60 patients will be enrolled at the rate of 3-4 patients per month. Stopping boundaries will be assessed in cohorts of 5 patients after a minimum of 10 patients have been enrolled. Response and toxicity will be monitored independently. The method of Thall and Simon will be employed to perform interim monitoring.

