##### **11.6.1 Primary Analysis**

The primary endpoint in this study is response defined as the percentage of subjects achieving a complete or partial tumor response using RECIST criteria. The response rate will be calculated from the view of best response that records confirmed cases of CR or PR. Subjects with unknown or missing response will be treated as non-responders; i.e., they will be included in the denominator when calculating the percentage. Response will be evaluated by the recist criteria 4 weeks (+/- 4 days) after completion of radiation therapy.

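### A sentence in 11.6.2, read literally, makes RECIST responders who stay inoperable non-responders for the primary endpoint; it should be limited to pCR

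*Combined protocol and SAP*

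**What the plan says.** **Primary endpoint.** Section 11.6.1 gives it as "response defined as the percentage of subjects achieving a complete or partial tumor response using RECIST criteria", counts confirmed responses, and sets the timing: "Response will be evaluated by the recist criteria 4 weeks (+/- 4 days) after completion of radiation therapy". Sections 1.0, 10.0 and 11.3 agree on RECIST response. Section 1.0 applies it to all patients who receive treatment and covers "Pre-operative or palliative concurrent radiation with capecitabine to the breast". None of these sections makes operability a condition.

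**Non-responders by rule.** Section 11.3 names patients who do not finish and adds: "Patients who are not evaluable for response will be considered non-responders". Section 11.6.1 names those with unknown or missing response. Neither mentions conversion to operable.

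**The sentence at issue.** Section 11.6.2, headed as the secondary analysis, first gives two routes by which a patient counts as converted. It then defines pCR. The pCR paragraph closes by adding to the unknown or missing cases that "those who do not convert to operable will be included in the primary efficacy analysis as non-responders".

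**Decision criterion.** Section 11.1: "The regimen will be considered of interest for further study if the response rate is at least 80" per cent, with a separate toxicity condition.

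**The concern.** Conversion to operable is a secondary objective (sections 1.0 and 10.0), yet this sentence appears to make it a condition of primary response. Consider a patient who is inoperable at entry, has a confirmed partial response and is never offered a mastectomy. Section 11.6.1 counts her as a responder; 11.6.2, taken at its word, does not. The protocol expects such patients: section 4.1 provides for those still inoperable at the surgical consultation, and section 6.0 allows pre-operative intent to be changed to palliative.

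If the sentence were applied to the primary endpoint, the final rate would measure response together with conversion. That is a different and smaller quantity than the RECIST rate that 11.1 sets against 80%. The error would run against the regimen. No text says which rule governs, so the choice could be left until the data are in hand.

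**Working it through.** **1. The texts side by side**

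| Patient inoperable at entry | 11.6.1 | 11.6.2, literal |
|---|---|---|
| Confirmed CR or PR, converts | responder | responder |
| Confirmed CR or PR, does not convert | responder | non-responder |
| SD or PD, does not convert | non-responder | non-responder |
| Response unknown or missing | non-responder | non-responder |

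The rules differ only in the second row. Let r be the number of patients in that row. The documents do not give r.

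**2. Timing**

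Primary response is read 4 weeks (within 4 days either way) after radiation. The second conversion route is for patients "who have a mastectomy and no FDG-avid disease on PET at 3 month follow up". Conversion by that route cannot be known when primary response is read, which suggests that the sentence was not written for the RECIST endpoint.

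**3. The plan's own figure**

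Inputs: N = 60 (11.3); prior for the response rate Beta(1.6, 0.4) and target Beta(80, 20) (11.3.1); example of 54 responses (11.3.3).

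Posterior after x responses in 60: Beta(1.6 + x, 0.4 + 60 − x).

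For x = 54 this is Beta(55.6, 6.4), with a 95% interval of 81.1% to 95.9%. This matches 11.3.3.

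**4. Effect of the sentence, for illustration**

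Set x = 54 − r. The last column is the 11.3.1 quantity Pr[R,E < R,S | data], found by numerical integration; the plan's cutoff is 0.95.

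| r | x/60 | Rate | 95% credible interval | Pr[R,E < R,S] |
|---|---|---|---|---|
| 0 | 54/60 | 90.0% | 81.1% to 95.9% | 0.043 |
| 6 | 48/60 | 80.0% | 69.3% to 88.9% | 0.492 |
| 7 | 47/60 | 78.3% | 67.4% to 87.6% | 0.591 |
| 13 | 41/60 | 68.3% | 56.7% to 79.5% | 0.947 |
| 14 | 40/60 | 66.7% | 55.0% to 78.1% | 0.966 |

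- The observed rate falls below 80% when (54 − r)/60 < 0.80, that is r > 6, so first at r = 7.
- The cutoff is first passed at x = 40, the boundary tabulated for 60 patients. This needs r = 54 − 40 = 14.
- For r from 7 to 13 the observed rate is under 80% but the 11.3.1 criterion is not met.

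**5. After the repair**

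With conversion kept out of primary response, no design figure changes. The 11 response boundaries, the 11 toxicity boundaries, the nine operating-characteristic rows and both credible intervals in section 11.3 all reproduce from the stated priors and cutoffs without any operability condition.

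**The case against.** **The sentence may concern pCR only.** This is the strongest point. Section 11.6 opens by assigning the ITT population to the primary analysis of efficacy and safety, and the surgical population to a secondary analysis of surgical efficacy. On that usage the sentence means that, in the ITT analysis of pCR, patients who never become operable count as failures. Its place in the pCR paragraph fits, as does the 3-month PET. The reading is plausible and may be what was intended. It is not stated, however. The wording names the primary efficacy analysis, and the next paragraph defines an evaluable-only response rate that drops unknown or missing responses, so the sentence can equally be taken as part of the RECIST rule.

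**Misapplication is unlikely and would be conservative.** Four sections agree on the endpoint, and the sentence sits under the secondary analysis. It could not produce a false claim of efficacy. Both points stand and limit the importance of the issue. They do not remove the conflict in wording.

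**Stronger readings that the documents do not support**

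- *Every patient who does not convert is a lost responder.* Non-converters with SD or PD are non-responders under either rule. The 91% and 82% conversion rates in section 3.5 therefore do not give r; in the 28-patient study, the five patients who had no surgery had all progressed.
- *Palliative patients cap the attainable rate.* This assumes that they cannot convert, but 11.6.2 lets some patients with M1 disease convert, and no palliative share is given.
- *The clause also removes responders who were not inoperable at entry.* Section 8.1 admits, for example, "Patients who have chemo-refractory gross disease in the breast causing symptoms (pain, drainage, duress) OR" with no inoperability requirement in that branch. Conversion is not defined for patients who were never inoperable, so even a literal reading need not reach them.
- *Second-route patients who refuse mastectomy are always reclassified.* This treats the two routes as exclusive. The second is worded as an addition, so a responder who was inoperable at enrolment and refuses an offered mastectomy may qualify by the first.
- *The stopping rules are compromised.* Section 11.3 takes response after 45 Gy for monitoring, before conversion is settled.

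**Conclusion.** The conflict in wording is real and should be fixed. As the text stands, a confirmed responder who is inoperable at entry and does not convert is classified in opposite ways by 11.6.1 and 11.6.2. Confidence is high that the wording conflicts; that it was meant for pCR is a reasonable inference and no more.

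If applied to the primary endpoint, the sentence would bias the final response rate downward. The size cannot be estimated from the documents. The counts of 7 and 14 reclassified responders rest on the plan's 54/60 example and an assumed r. The count of 7 also takes the 80% in 11.1 as a threshold for the observed proportion, whereas 11.3 speaks of a high probability of falling below 80% and 11.3.3 promises a posterior distribution.

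**What to change.** In 11.6.2:

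1. Limit the operability clause to pCR, for example: patients with unknown or missing pCR status, and those who do not convert to operable, are included in the ITT analysis of pCR as not having pCR.
2. State that conversion to operable plays no part in primary RECIST response, and that the non-responder rules of 11.3 (did not finish, not evaluable) and 11.6.1 (unknown or missing) are the only ones for that endpoint.
3. State that the ITT pCR rate uses all treated patients, and that the rate in the surgical population (sections 10.0, 11.5 and 11.6) is the separate secondary analysis.

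Deleting the clause outright would be less good, because non-converters would then have no stated rule in an ITT analysis of pCR.

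The cost is a few sentences. No further patients, data or procedures are needed, and no boundary or operating characteristic changes.
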